The action taken regarding the study treatment (corneal cross-linking) must be clarified in the CRF as follows:

- None.
- Study product not applied.
- Unknown.

Adverse Event treatment required

The need for any treatment to solve the adverse event must be clarified in the CRF as follows:

- None (other than protocol therapy).
- Drug therapy.
- Non-drug therapy.
- Hospitalization.

Outcome of Adverse Event

The outcome of an event will be classified as follows:

- Recovered.
- Recovered with sequelae.
- Ongoing.
- Fatal.
- Unknown/Lost to follow-up.

Serious Adverse Event Reporting

Any AE considered serious by the principal investigator of the Site of Investigation must be reported to IEC and the Sponsor within 24 hours from the time site personnel first learn about the event and during normal business CET hours.

A written report must be submitted within 24 hours of the initial reporting to the IEC and the Sponsor and should consist of the Serious Adverse Event Report Form, accompanied by the following CRF

pages: the demographics page(s), the medical history page(s), the AE page(s) and the concomitant medications page(s). If the participant is hospitalized because of or during the course of an SAE, then a scanned copy of the hospital discharge summary should be sent by email to Sponsor as soon as it becomes available. Withdrawal from the study and all therapeutic measures will be at the discretion of the principal investigator. All SAEs (related or unknown relationship to the study Treatment) will be followed until satisfactory resolution or until the principal investigator or investigator deems the event to be chronic or the participant to be stable.

The Principal Investigator of Site of Investigation will be responsible for telephone or fax reporting of any SAE to the IEC. Site will notify the IEC by telephone or fax transmission of any unexpected, fatal, or life-threatening experience (expedited report) associated with the use of the study Treatment as soon as possible but no later than 7 calendar days after the initial receipt of the information. Initial notification will be followed by a written report within 15 calendar days. For unexpected events associated with the use of the study Treatment, Sponsor/CRO will notify the IEC as soon as possible, but no later than 15 days of the initial receipt of information. The principal investigator is responsible for informing the Ethical Committee. Copies of SAE correspondence with the principal investigator or investigators, governing authorities, ethics committees, and the sponsor must be submitted to Sponsor/CRO for filing.

Adverse Event Monitoring

A participant experiencing any AE or SAE will receive treatment and follow-up evaluations by the principal investigator of the Site of Investigation or will be referred to another appropriate physician for treatment and follow-up. All AEs, whether serious or non-serious, should be followed to resolution or until the AE is determined by the investigator not to be clinically significant.

List of adverse events reported in the specialized literature after CXL treatment

Summary of adverse events on total 9607 cases treated by CXL procedures (ref. bibliography)				
N	Type of adverse event	Intensity of adverse event	Cases (n.)	Incidence (%)
1	Bacterial keratitis	Severe	59	0.61%
2	Herpetic keratitis		5	0.05%
3	Corneal burn		1	0.01%
4	Corneal scarring		51	0.53%
5	CDVA loss (>2 ETDRS lines)		13	0.13%

6	Persistent corneal haze	Moderate	12	0.12%
7	Corneal infiltrates		54	0.56%
8	Epithelial ingrowth under LASIK flap		1	0.01%
9	Eyelid eczema	Mild	1	0.01%
10	Transient eye pain		18	0.19%
11	Transient ocular itching		1	0.01%
12	Transient visual fogging		16	0.17%
13	Dry eye		6	0.06%
14	Conjunctival hyperemia		10	0.10%
15	Transient corneal haze		499	5.19%
16	Transient corneal edema		74	0.77%

The table above shows the adverse events reported in studies of eyes treated both by Epi-Off and Epi-On corneal cross-linking procedures. In these studies, the majority of AEs generally developed in the short-term. The percentage of AEs that resolved by 3 months study visit was 98%. The most common AEs (i.e., $\geq 10\%$) were corneal epithelium defect, corneal opacity, corneal edema/striae, eye pain, and punctate keratitis. Most of these events represented sequelae following corneal epithelial debridement. Indeed, the Epi-Off corneal cross-linking procedure involves removal of the corneal epithelial layer, which is expected to result in reduction of vision due to the injury to the epithelium. The reduction in visual function and other adverse reactions generally resolve with the healing of the epithelium by the first week after treatment, though visual recovery to baseline values may take up to 3 months after treatment.

Treatment strategy for adverse events

Any adverse event is monitored in order to respond promptly and adequately to each of them. Since all participants will administer antibiotic/disinfectant eye drops and lubricant eye drops immediately after dosing and treatment, the majority of adverse event is managed preventively according to the standard of care after corneal cross-linking. The use of anti-inflammatory eye drops may be required in the case of moderate or severe ocular surface inflammation in a participant. The use of paracetamol pills may be used in the event of unacceptable headache in a participant.

[figure not shown]
Statistical Considerations and Data Analysis

Stratification, Allocation and Enrolment

Eligible participants will be stratified with allocation ratio 1:1 into either theranostic-guided CXL treatment protocol using a computer-generated stratification plan with blocks. Two different blocks are created, which include eyes with K_{max} steeper or flatter than 54.0 D to stratify patients with comparable baseline K_{max} values in either theranostic-guided CXL treatment protocol.

This is a multi-center clinical trial. The stratification code is given to each local site of investigation by the central monitoring site of the Sponsor after the participant has been considered eligible to the study and has signed the informed consent. The enrolment is competitive. The period for enrollment includes the four months after study protocol approval by the IEC of the local site of investigation.

Synopsis on disposition of participants

Sample size

By expecting a response rate of 50% of cases that will reach the threshold of -1.05 D of the K_{max} value, a sample size of 42 patients achieves 91% power to detect a difference of 0,25 between the area under the ROC curve (AUC) under the null hypothesis of 0,60 and an AUC under the alternative hypothesis of 0,85 using a two-sided z-test at a significance level of 0,05000. The data are continuous responses. Considering a $\leq 20\%$ drop-out rate (determined from systematic literature review on controlled and open clinical studies on standard and epithelium-on CXL procedures), a number of 50 participants (25 per treatment protocol) is allowed to be enrolled in the study.

Details on the methodology and process used to define the sample size of this clinical trial are described in Appendix 1 – Methodology for sample size calculation.

Statistical methodology

Descriptive statistics will be used to summarize the data: numerical variables will be summarized as mean and standard deviation or median and interquartile range, respectively, according to the distribution of the data; categorical variables will be represented as frequencies and proportions. Student's t-test or Wilcoxon test will be applied to compare continuous variables, while Fisher's exact test or Chi-Squared test will be used to analyze categorical variables. Bonferroni correction is applied to analysis of exploratory outcome measures of stratification groups. For all reported AEs, the data can be presented with events listed in order of decreasing frequency.

The optimal cut-off values in predicting the propensity of CXL treatment to flatten the Kmax value at 12-months was determined based upon the results of preclinical studies (data not disclosed to investigators to avoiding methodological study bias) and can be optimized with the Youden index. The accuracy and precision (95% CI) of the combined use of the theranostic imaging biomarkers to predict CXL treatment outcome will be determined by calculating the proportion of correctly classified eyes and the positive predictive value (PPV) respectively. The miss rate, which is the probability that a true positive is missed by the theranostic methodology, will be determined by calculating the false negative rate (FNR).

Statistical significance will be set at 0.05. All the analysis will be performed using the statistical software R (latest version available).

Population to be analysed

The **Intent-to-Treat (ITT) Population** consists of all participants who were enrolled into the trial and performed at least 1 follow-up visit.

The **Per Protocol (PP) Population** will be a subset of the ITT population and will consists of all participants who participated and completed at least 66% of all the visits (i.e., 4 of 6 total visits) and the last visit 6 at day-360 and in whom there are no major protocol deviations.

Both populations will be agreed upon by Sponsor, Principal Investigator/Site of Investigation after the final subject visit and in advance of the database lock.

Ethical and Regulatory Issues

This study adheres with the ethical principles that have their origin in the Declaration of Helsinki (Seventh revision, 2013), the Convention of Oviedo, April, 4th 1997, and is consistent with GCP, including the ICH Guideline for good clinical practice E6, the Directive 2001/20/EC, the ISO 14155:2011, the Regulation (EU) 536/2014 of the European Parliament and of the Council of 16 April 2014, the Regulation (EU) 2017/745 of the European Parliament and of the Council of 5 April 2017, the Ministerial decree of the Italian Minister of Health of 2 August 2005, the Decree n.211 of 24 June 2003, the Ministerial Decree of 14 July 2009 and applicable regulatory requirements concerning human subject protection and other aspects of clinical investigations.

The study is conducted in strict compliance with the study protocol; any revision to study protocol must be discussed with and prepared by the Sponsor. The Investigator should not implement any deviation or change to the protocol without prior review and documented approval/favorable opinion from the Sponsor and IEC of an amendment. Any significant deviation must be documented in the CRF.

Good Clinical Practice (GCP) for Clinical trials

The Study will be conducted in accordance with the 13 principles of the rules of good clinical practice, as described below:

- 1) The study complies with the principles of the Declaration of Helsinki.
- 2) The expected benefits to participants justify the risks.
- 3) The rights, safety, and well-being of the participants to the trial are the most important considerations and prevail over those of science and society.
- 4) The available information about the investigational product are adequate to support the proposed clinical trial.
- 5) The clinical study is drafted according to strong technical and scientific background and is fully described in the study protocol.
- 6) The study will be conducted in accordance with the study protocol only after approval of the ethical committee.
- 7) The medical care given to, and the medical decisions made on behalf of the participants will always fall under the responsibility of qualified medical specialists.
- 8) All the investigators have the education, training, and experience to perform their specific tasks.
- 9) An informed consent should be freely obtained by each participant prior to his participation in the study.

- 10) Any information concerning the clinical study is recorded, handled, and stored in a way that allows its accurate reporting, interpretation and verification.
- 11) The confidentiality of the documents is ensured by respecting the privacy and confidentiality rules provided for by the applicable regulatory requirements.
- 12) The investigational products are manufactured, handled, and stored in compliance with good manufacturing practice applicable and are used according to the approved protocol.
- 13) Procedures are implemented to guarantee the quality of every aspect of the trial.

Independent Ethics Committee approval

The International Conference on Harmonisation (ICH) guidelines require that approval be obtained from an independent ethical committee (IEC) prior to participation of human participants in research studies. Prior to the study onset, the protocol, informed consent, advertisements to be used for participant recruitment, and any other written information regarding this study to be provided to the participant must be approved by the IEC. Documentation of all IEC approvals and of the IEC compliance with ICH Guideline E6 will be maintained by the site and will be available for review by the sponsor or its designee.

The Principal Investigator/Site of Investigation and CRO, if applicable, will support the Sponsor in answering question from the IEC in relation to the study or study procedures.

All IEC approvals should be signed by the IEC Chairman or designee and must identify the IEC name and address, the clinical protocol by title and/or protocol number and the date approval and/or favorable opinion was granted.

The study may only begin after approval of the same committee. Before initiating the clinical trial, the Principal Investigator/Site of Investigation should have written and dated approval/favorable opinion from the IEC for the trial protocol.

Informed consent

A written informed consent (Annex 3) shall be obtained from each participant prior to entering the study or performing any unusual or non-routine procedure that involves risk to the participant. An informed consent template may be provided by the sponsor to investigative sites. If any institution-specific modifications to study-related procedures are proposed or made by the site, the consent should be reviewed by the sponsor and/or its designee, if appropriate prior to IEC submission. Once reviewed, the consent will be submitted by the Principal Investigator/Site of Investigation to the IEC for review and approval prior to the start of the study. If the informed consent form is revised during the course of the study, all active participating participants must sign the revised form.

Before recruitment and enrollment, each prospective participant will be given a full explanation of the study and allowed to read the approved informed consent form. Once the Principal Investigator/Site of Investigation is assured that the participant understands the implications of participating in the study, the participant will be asked to give consent to participate in the study by signing the informed consent form.

The Principal Investigator/Site of Investigation shall provide an original form of the signed informed consent to the participant. A second original form shall be maintained in the participant's medical records at the site.

Risk Assessment and Management

The present study does not accept healthy volunteers. Participants who are eligible to the study are those affected by keratoconus.

This particular study design assumes that the theranostic-guided riboflavin/UV-A corneal cross-linking treatment does not induce in the participants unacceptable risks. Several clinical studies^{10,11,12,13,14} have shown safety and efficacy of corneal cross-linking using a 0.2% riboflavin ophthalmic solution to protect the cornea prior to UV-A irradiation. The occurrence of severe adverse events, such as ulcerative keratitis, have been registered in 0.2% of Epi-OFF CXL procedures; no severe adverse events have been recorded after Epi-ON CXL procedures.

The safety of participants has been assessed according to the following issues:

1. The use of CE marked medical devices for the indication of use;
2. the risks inherent in the type and route of administration of the products;

The seriousness of possible adverse reactions and the probability of them happening have been considered during study design and listed under "Adverse Events" section. The innovative corneal cross-linking procedure is expected to elevate the gold standard practice by improving predictability of CXL clinical outcome and thus to provide adequate therapeutic benefit to justify entering keratoconus patients into the study. The management of the possible adverse reactions has been described under "Adverse Events" section.

The Sponsor has given the Principal Investigator/Site of Investigation and IEC full access to the relevant pre-clinical work on the medical devices in the Investigator's Brochure (Annex 8). The

¹⁰ Zhang X, Sun L, Chen Y, Li M, Tian M, Zhou X. One-year outcomes of pachymetry and epithelium thicknesses after accelerated (45 mW/cm²) transepithelial corneal collagen cross-linking for keratoconus patients. *Sci Rep* 2016;6:32692.

¹¹ Artola A, Piñero DP, Ruiz-Fortes P, Soto-Negro R, Pérez-Cambró RJ. Clinical outcomes at one year following keratoconus treatment with accelerated transepithelial cross-linking. *Int J Ophthalmol* 2017;10(4):652-655.

¹² Tian M, Jian W, Sun L, Shen Y, Zhang X, Zhou X. One-year follow-up of accelerated transepithelial corneal collagen cross-linking for progressive pediatric keratoconus. *BMC Ophthalmol* 2018;18(1):75.

¹³ Kir MB, Türkyılmaz K, Öner V. Transepithelial high-intensity cross-linking for the treatment of progressive keratoconus: 2-year outcomes. *Curr Eye Res* 2017;42(1):28-31.

¹⁴ Huang J, Shen Y, Jian W, Xu H, Li M, Zhao J, Zhou X, Liao H. Two-year topographic and densitometric outcomes of accelerated (45 mW/cm²) transepithelial corneal cross-linking for keratoconus: a case-control study. *BMC Ophthalmol* 2018;18(1):337.

medical devices have been shown to be designed and manufactured according to the Directive 93/42/CE and to be further safe for the indication of use in pre-clinical and regulatory testing.

The Sponsor ensures for the entire duration of the study to monitor the safety of subjects by strict assessment of the risks inherent in the type of medical device and its target and in any potential immediate toxicity predicted from non-clinical or literature information.

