Theranostics is an emerging therapeutic paradigm that enables monitoring of image-guided therapy in clinic through the use of a theranostic module that makes use of real-time non-invasive molecular analysis of the tissue being treated to achieve optimal treatment outcomes in the management of disease.

This is a clinical study consisting of a study arm to assess the performance of the theranostic software module (Research Use Only) of a CE marked (CE1936) UV-A medical device, C4V CHROMO4VIS™, in order to validate its use for image-guided corneal cross-linking treatment of keratoconus and corneal ectasia. The study hypothesis is that theranostic-guided riboflavin/UV-A corneal cross-linking with the C4V CHROMO4VIS™ system is safe and can estimate treatment efficacy during operation, regardless of treatment protocol, i.e., either with or without epithelial

removal. The software module is able to measure the concentration of riboflavin into the cornea during treatment and to provide the surgeon with an objective assessment of treatment efficacy. The scope of this study is to validate the theranostic imaging biomarker score by assessing the change of corneal topography K_{max} value at 1-year postoperatively. The 1-year follow-up is long enough to provide scientific evidence of the safety and efficacy of the theranostic UV-A medical device in question. A pre-operative examination will ensure that every interested and willing participant fulfils the inclusion criteria of this study. Post-operative examinations will be carried out after 1 week, 1 month, 3 months, 6 months and 12 months.

The present study can start treatment of subjects only after an Independent Ethical Committee written approval; it is governed by three guiding principles: safety, ethical conduct, and efficiency. Subject safety guides study design by minimizing the number of participants exposed to serious adverse events.

Abbreviations

AE	Adverse Event
CDVA	Corrected Distance Visual Acuity
C4V CHROMO4VIS™	Theranostic UV-A medical device
C4V	Theranostic UV-A medical device acronym
CFR	Code of Federal Regulation
CRF	Case Report Form
CRO	Contract Research Organization
CTA	Clinical Trial Authorization
CV	Curriculum Vitae
CXL	Corneal cross-linking
D	Diopter
EpiOFF	Epithelium off
EpiON	Epithelium on or transepithelial
GCP	Good Clinical Practice
GDPR	General Data Protection Regulation
GMP	Good Manufacturing Practice
ICH	International Council for Harmonization
IEC	Independent Ethical Committee

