Study objective

The scope of the study is to evaluate a novel modality of riboflavin/UV-A corneal cross-linking based on theranostics aiming at improving predictability of treatment efficacy for better patient care. The objective of the study is to validate the theranostic imaging biomarkers by assessing the mean change of K_{max} value at 12 months after riboflavin/UV-A corneal cross-linking for the treatment of keratoconus.

Study design

Subjects with a diagnosis of progressive keratoconus will be evaluated for suitability as a candidate for riboflavin/UV-A corneal cross-linking. Participants will be evaluated at baseline, day 0 (treatment), day 7, day 30, day 90, day 180 and day 360 after treatment. Informed consent will be obtained from each subject before performance of any required procedures.

Eye examination

Each study participant will undergo at baseline and at each follow-up visit:

- Uncorrected Distance Visual Acuity (UDVA) with ETDRS chart.
- Corrected Distance Visual Acuity (CDVA) with ETDRS chart.
- Manifest Spherical Equivalent Refraction (MSER) with ETDRS chart.

- Maximum Simulated Keratometry (K_{max}) and Central Corneal Thickness (CCT) with combined corneal topography and pachymetry.
- Endothelial Cell Density (ECD) with corneal specular microscopy.
- Slit-lamp examination of the cornea, anterior chamber and lens.

Study arm

One study arm receiving riboflavin/UV-A corneal cross-linking with either standard, Epi-OFF, or transepithelial, Epi-ON, treatment protocol. Only one eye of each participant is designated as the study eye.

Stratification, Allocation and Enrolment

Eligible participants will be stratified with allocation ratio 1:1 into either treatment protocol using a computer-generated stratification plan with blocks. Two different blocks are created, which include eyes with K_{max} steeper or flatter than 54.0 D to allocate patients with comparable baseline K_{max} values in either treatment protocol.

This is a multi-center clinical trial. The stratification code is given to each local site of investigation by the central monitoring site of the Sponsor after the participant has been considered eligible to the study and has signed the informed consent. The enrolment is competitive. The period for enrollment includes the four months after study protocol approval by the IEC of the local site of investigation.

Sample size

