- During the application phase, the system tracks the application time of riboflavin and notifies the user that the induction is complete. The system provides the Operator with an index estimating the concentration of riboflavin into the cornea.
 - EpiOFF protocol: before measuring the riboflavin concentration into the cornea, dry the corneal surface with a tnt stick.
 - EpiON protocol: before measuring the riboflavin concentration into the cornea, rinse the corneal surface with balanced salt solution.
- The UV-A treatment is then performed. The device tracks the UV-A treatment time, turns off the UV-A and notifies the user when the treatment has been completed. The system provides the Operator with an index estimating the treatment efficacy, i.e., the theranostic imaging biomarker.
 - The operator may choose to rinse the corneal surface with balanced salt solution at 5 minutes interval during UV-A irradiation.
- Once the treatment has been completed, the Operator save the treatment report in a USB stick for printing and adding it to the medical patient record.
- The Operator may choose to treat another eligible patient or the device may be powered off.

Pre-clinical studies on safety of the UV-A medical device

[figure not shown]
The C4V CHROMO4VIS system has been designed and built in full compliance with EU Directive 93/42/EEC. The medical device has undergone safety testing according to the following standards:

- EMC EN 60601-1-2
- EN 60601-1
- ISO 15004-2:2007
- EN 64271:2010

Results of the emission and immunity testing

[REDACTED]	[REDACTED]	[REDACTED]	[REDACTED]	[REDACTED]	[REDACTED]
[REDACTED]	[REDACTED]	[REDACTED]	[REDACTED]	[REDACTED]	[REDACTED]
[REDACTED]	[REDACTED]	[REDACTED]	[REDACTED]	[REDACTED]	[REDACTED]
[REDACTED]	[REDACTED]	[REDACTED]	[REDACTED]	[REDACTED]	[REDACTED]
[REDACTED]	[REDACTED]	[REDACTED]	[REDACTED]	[REDACTED]	[REDACTED]

Pre-clinical studies on efficacy of the theranostic UV-A medical device

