- Once the UV-A energy dose and irradiance have been set, the system calculated the UV-A irradiation treatment time in minutes and seconds;
- the user adds the key code of the eligible patient to be treated in the “patient database screen” of the system;
- the user add the eye to be treated and the corneal parameters (CCT and K_{max}) in the “treatment plan screen” of the system and confirm to begin treatment;
- the user prepares the patient’s eye for treatment (numbing eye drops and eye speculum) and access the “treatment screen” of the C4V CHROMO4VIS™ system;
- the user applies the riboflavin ophthalmic solution onto the cornea; the user applies one drop of riboflavin every 20 seconds directly onto the cornea of the eye to treat;
- the user must dry (in EpiOFF protocol) or rinse with balanced salt solution (in EpiON protocol) the excess of riboflavin onto the cornea before measuring its concentration by pressing the foot switch;
- the C4V CHROMO4VIS™ system tracks the riboflavin application time and notifies the user that the induction is complete;
- the user selects to proceed to perform UV-A treatment in the “treatment screen” of the C4V CHROMO4VIS™ system;
- the user may choose to rinse with a drop of balanced salt solution the corneal surface during UV-A irradiation once at 5 minutes interval.
- the C4V CHROMO4VIS™ system tracks the UV-A treatment time, turns off the UV-A and notifies the user when the treatment has been completed;
- the user saves the treatment report in an USB stick;
- the user may choose to treat another eligible patient or the C4V CHROMO4VIS™ system may be powered off.

Detailed information on the treatment procedure can be found in the User Manual – For Research Use Only (Annex 9), including the pictures of the wizard screens.

Patient Counseling Information

Patients shall be advised not to rub their eyes for the first week after their procedure.

Patients may be sensitive to light and have a foreign body sensation. Patients shall be advised that there may be discomfort in the treated eye and that sunglasses may help with light sensitivity.

If patients experience severe pain in the eye or any sudden decrease in their vision, they shall be advised to contact the Principal Investigator of the Site of Investigation immediately.

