- Measurement of **corneal endothelial cell density** (ECD) with specular microscopy will assess will assess changes of the ECD after treatment.
- **Slit lamp biomicroscopy** will assess integrity of the cornea and anterior segment of the eye.

Primary outcome measure

Validation of the Theranostic Imaging Biomarker [Time Frame: 12-months]

- Validation of the combined use of the theranostic imaging biomarkers. True positives, false positives, true negatives and false negatives were evaluated in order to determine the ability of the theranostic imaging biomarkers, including both the *riboflavin score* and *theranostic score*, to predict the propensity of CXL treatment in flattening the K_{max} value (D) by more than 0.1 D at 12 months postoperatively.

Theranostics: confirmation of the theranostic imaging biomarker will be provided at the end of treatment procedure. The theranostic data, which will be recorded during treatment procedure, will be exported to a computer for subsequent analysis with 12-months data.

The accuracy and precision (95% CI) of the combined use of the theranostic imaging biomarkers to predict CXL treatment outcome were determined by calculating the proportion of correctly classified eyes and the positive predictive value (PPV) respectively. The miss rate, which is the probability that a true positive is missed by the theranostic methodology, was determined by calculating the false negative rate (FNR).

The study sets a minimum threshold of 85% for the theranostic software module's accuracy and precision in predicting the propensity of CXL to halt disease progression (intended as more than 0.1 D Kmax flattening) at 1 year in the study population, who participated and completed at least 66% of all the visits (i.e., 4 of 6 total visits) and the last at 12 months (i.e., Per Protocol Population);

Secondary outcome measures

Efficacy [Time Frame: 12-months]

- Change of Maximum Keratometry index assessed by corneal topography at 12-months.

Corneal topography: measurement of maximum simulated keratometry (K_{max} , D) will be done by using Placido disk corneal topography. The investigator will record the K_{max} value at each visit and will fill the corresponding CRF. This test is performed to provide evidence of corneal curvature change after treatment.

Safety [Time Frame: 12-months]

- Change of Endothelial Cell Density assessed by specular microscopy at 12-months.

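### The plan promises improved predictability of cross-linking outcome, but no planned analysis compares the scores with what is known before treatment, so meeting the 85% criterion validates classification without showing improvement

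*Combined protocol and SAP*

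**What the plan says.** The Synopsis (Study objective) describes a modality "aiming at improving predictability of treatment efficacy for better patient care", and the Aim in the Study Plan repeats the idea. Risk Assessment and Management says the procedure "is expected to elevate the gold standard practice by improving predictability of CXL clinical outcome" and uses this to justify entering patients. The section on the theranostic software module wants a biomarker threshold that holds whichever protocol is used.

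The operational objective, stated in the same places, is to validate the scores. The event to be predicted is Kmax flattening "by more than 0.1 D at 12 months postoperatively". The criterion, in Primary outcome measure, begins "The study sets a minimum threshold of 85% for the theranostic software" and applies to accuracy (proportion of eyes correctly classified) and precision (PPV) in the per-protocol population. The Sample size section tests an AUC of 0.85 against a null of 0.60 in 42 eyes. Statistical methodology says the cut-offs come from preclinical work and may be optimised with the Youden index.

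Allocation to Epi-OFF or Epi-ON is 1:1 and known before treatment. Kmax and CCT are measured at baseline and entered into the device beforehand. Both protocols use preset soak times and UV-A settings. The operation sequence places the efficacy index at the end of irradiation: "The system provides the Operator with an index estimating the treatment efficacy, i.e., the theranostic imaging biomarker".

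**The concern.** Improvement needs a reference, and the plan has none. The ROC analysis, sensitivity, specificity, accuracy, PPV and false negative rate all describe the scores alone. The pre/post tests concern Kmax and the other measurements. No analysis asks whether the scores classify better than the responder rate, the protocol, or baseline Kmax and CCT.

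The protocol matters most here, because Appendix 1 itself reports different one-year Kmax changes for the two techniques. In a pooled analysis of both protocols, a score can separate responders from non-responders partly by identifying which protocol the eye received. At stake is what the final report may conclude: that the scores predict 12-month flattening, or that they improve on existing knowledge, which is the stated aim and benefit.

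**Working it through.** **The plan's own figure.** With 21 responders and 21 non-responders, the Hanley-McNeil variance gives SE 0.0880 at AUC 0.60 and 0.0608 at AUC 0.85. Power = Φ((0.25 − 1.96 × 0.0880)/0.0608) = 89.9%, close to the stated 91%. The calculation is sound for a fixed null of 0.60. The question is what that null represents.

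**Inputs from Appendix 1 (one-year Kmax change).** Pooled: −1.05 ± 0.80 D. Standard: −1.41 ± 1.71 D. Transepithelial: −0.32 ± 1.55 D. Assumptions: changes are normally distributed, and these literature results carry over to this trial's presets.

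**Share of eyes flattening by more than 0.1 D**, Φ((−0.1 − mean)/SD):
- Epi-OFF: Φ(1.31/1.71) = 77.8%
- Epi-ON: Φ(0.22/1.55) = 55.6%
- 1:1 mix: (77.8 + 55.6)/2 = 66.7%
- Pooled figure: Φ(0.95/0.80) = 88.2%

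**Rule 1: protocol only (Epi-OFF = responder).**
- PPV = 77.8%
- Accuracy = (0.778 + 0.444)/2 = 61.1%
- Sensitivity = 0.778/(0.778 + 0.556) = 0.583
- Specificity = 0.444/(0.222 + 0.444) = 0.667
- AUC = (0.583 + 0.667)/2 = 0.625

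This rule slightly exceeds the null AUC but misses both parts of the 85% criterion.

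**Rule 2: call every eye a responder.** Accuracy and PPV both equal the responder rate. With 42 eyes the bar is 0.85 × 42 = 35.7, so 36 eyes. Exact binomial probability of reaching it:
- responder rate 88.2%: 78%
- responder rate 66.7%: about 0.5%

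The two sets of figures in the same appendix therefore give opposite answers on whether the bar can be met with no information.

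**Could a score stand in for the protocol?** In the third pre-clinical study, riboflavin after soaking was 425 ± 77 µg/cm³ with the epithelium off and 195 ± 35 µg/cm³ transepithelially. Under normality, an epithelium-off cornea exceeds a transepithelial one with probability Φ(230/√(77² + 35²)) = Φ(230/84.6), about 0.997. This is only an indication: there were five corneas per group, and the transepithelial soak used iontophoresis, not this trial's drops.

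**What a comparison could show with 42 eyes.** Suppose the scores reach 85% accuracy and their errors are independent of the rule's errors (an assumption). With a = 0.85 and b the rule's accuracy, SE = √{[a(1 − b) + (1 − a)b − (a − b)²]/42}.

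| Reference rule | b | Gain (points) | SE (points) | 95% CI (points) |
|---|---|---|---|---|
| Protocol only | 61.1% | 23.9 | 9.3 | 6 to 42 |
| All responders, 1:1 mix | 66.7% | 18.3 | 9.1 | 0.4 to 36 |
| All responders, pooled figure | 88.2% | −3.2 | 7.4 | −18 to 11 |

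For a paired AUC comparison (score AUC 0.85, pre-treatment AUC 0.60 to 0.70, correlation 0.3 to 0.5, all assumed), power is 42% to 89% at 50% to 67% responders and 26% to 61% at 88%.

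**The case against.** The sponsor can fairly answer that the formal objective is validation. The sentences on improvement describe what the modality is for, the primary conclusion required in the Reports section is only that the scores predict flattening, and the background says no current option gives predictable outcomes. This stands as a defence of the primary analysis. It does not support keeping the improvement wording as an aim and as a benefit to participants.

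Some stronger readings are tempting, but the documents do not support them:
- **That the bar can be met just by knowing the protocol.** On the protocol-specific figures it cannot (61% and 78%). Reaching 85% there would point to a gain over protocol. What would remain open is Kmax and CCT, for which the documents give no predictive value.
- **That results by protocol would reveal nothing.** The Synopsis lists the primary outcome by stratification group as exploratory. If the groups are the protocols, discrimination within each cannot come from knowing the protocol. The Reports section, however, lists only secondary outcomes by group.
- **That error in the entered Kmax contaminates both score and outcome.** Whether the algorithm uses that entry is not stated. The same entry appears in the general device operation, so it is not evidence that the score uses it.
- **That nothing measured affects treatment.** The Treatment section makes access to UV-A depend on a minimum riboflavin concentration. Only the efficacy index comes too late to act on.

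A further fair objection concerns the remedy. A freely refitted model with protocol, Kmax, CCT and two scores would be optimistic. In 3,000 simulated trials of 42 eyes at the Appendix 1 rates, with Kmax, CCT and both scores pure noise, adding the scores raised the apparent AUC in 88% of runs, by 0.04 on average.

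**Conclusion.** The concern holds in a limited form. Meeting the 85% criterion would validate classification. It would not show improved predictability, because nothing planned supplies a comparison with pre-treatment knowledge. How far this matters depends on the responder rate. At the pooled 88%, a rule with no information is expected to exceed the bar. At the 67% mix, the bar is demanding and the open question narrows to Kmax and CCT. The null AUC of 0.60 is no safeguard, since protocol alone is at about 0.62.

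These sizes rest on normality and on literature results carried over to this trial's presets. They do not show that the scores lack added value; the plan simply would not establish it. Nor can the design show that score-guided treatment is better, since there is no unguided comparator. This is an inexpensive improvement, and the validation aim is not invalidated without it.

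**What to change.** In Primary outcome measure and Statistical methodology, keep the preclinically set cut-offs for this comparison (cut-offs tuned on the same eyes would favour the scores) and prespecify on the same eyes:

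1. Accuracy and PPV of the scores beside the call-all-responders and protocol-only rules, with the paired difference in accuracy and its 95% CI.
2. Score AUC within each protocol, and a protocol-stratified AUC.
3. As exploratory only, the gain over protocol, baseline Kmax and CCT, from a penalised or optimism-corrected model.

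State that improved predictability will be claimed only if the 95% CI for the gain in item 1 excludes zero in favour of the scores against both rules, and that the claim then names those rules as the reference. Otherwise conclude only that the scores predict 12-month flattening at the two fixed presets. In either case make no claim that score-guided treatment is better. Align the wording in Study objective, Aim, and Risk Assessment and Management.

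State whether the score algorithm uses the entered Kmax. Only if it does, add a sensitivity analysis that takes the outcome's baseline from the other scheduled topography reading (baseline visit or day 0).

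The cost is a short added analysis on data already collected, plus a few sentences. The downside is that the gain will be imprecise with about 42 eyes, and the claim may be narrower than the sponsor hopes.
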